8.1.3. Vitiligo Noticeability Scale (VNS)

The VNS is the subject's assessment of the noticeability of facial vitiligo determined at Visits 5, 6, 7, 8, 9, 10, 11 (if applicable) and if continuing for an additional 24 weeks of treatment, Visit 12-15. The subject will complete the following question:

Compared to before treatment, how noticeable is the vitiligo now?

- More noticeable (1)
- As noticeable (2)
- Slightly less noticeable (3)
- A lot less noticeable (4)
- No longer noticeable (5)

Treatment success will be defined as follows: VNS score of 1 or 2 = treatment not successful, VNS score of 3 = treatment partially successful, or VNS score of 4 or 5 = treatment successful.

8.1.4. Vitiligo Area Scoring Index (VASI)

The VASI will be assessed by the investigator or designee to track the total body vitiligo status throughout the study at screening (Visit 1), baseline (Visit 2), Week 12 (Visit 7), Week 24 (Visit 10), and Week 48 (Visit 14). The body is divided into the following 6 separate and mutually exclusive sites: head/neck, hands, upper extremities (excluding hands), trunk, lower extremities (excluding feet), and feet. The investigator or designee will assess each of the 6 body sites using a Wood's lamp to assist in the identification of the vitiliginous lesions.

The percentage of vitiligo involvement for each body region is calculated using the palmar method. The palmar method uses the palmar surface area of the investigator or designee's hand as an estimation guide and defines the surface of the evaluator's hand including fingers to be 1.0% of the total body surface area. Each of the 6 body sites is then clinically evaluated by visual assessment for the pattern of skin depigmentation using a visual scale. The publication by Hamzavi I, Jain H, McLean D, Shapiro J, Zeng H, and Lui H. 2004 will be provided to the investigators to depict the pattern of depigmentation as illustrated in descriptive patient photographs.

Total body VASI = Sum of all the values from the body sites (in Hand units) x (Residual depigmentation)

- **Hand unit** - One hand unit is approximately 1% BSA – used as a guide to estimate % of vitiligo involvement in each body area. (Body is divided into 6 areas)
- **Extent of residual depigmentation** is expressed by the following percentages:
 - 0
 - 10% - only specks of depigmentation are present
 - 25% - the pigmented area exceeds the depigmented area
 - 50% - the depigmented and pigmented areas are equal
 - 75% - the depigmented area exceeds the pigmented area
 - 90% - specks of pigment are present
 - 100% - no pigment is present

8.1.5. Subject Vitiligo Satisfaction Scale (SVSS)

The SVSS is the subject's assessment of her/his satisfaction with the status of the overall repigmentation of the treated areas of the face with vitiligo, at a particular point in time (See APPENDIX 5). The subject should NOT refer to any other assessments to assist with these assessments.

At Visits 7-10, and if applicable, Visit 11 and Visits 12-14, the subject will assess the treatment areas of the face with vitiligo using the scale below and report the one integer that best describes her/his satisfaction with the status of the repigmentation of the treated areas of his or her face.

Please report the number that best describes how satisfied you are with the results of the study medication applications on the treated areas of the face.

How satisfied or dissatisfied are you with the appearance of your facial vitiligo as a result of the study medication applications?

Subject's Vitiligo Satisfaction Scale

Grade	Descriptor
1	Extremely satisfied
2	Moderately satisfied
3	A little satisfied
4	Neither satisfied or dissatisfied
5	A little dissatisfied
6	Moderately dissatisfied
7	Extremely dissatisfied

An investigational staff member will educate the subject on the SVSS scale before each evaluation and direct the subject to assess the treated areas of the face. The staff member should not influence the subject's assessment.

The study staff member will report the SVSS grade the subject indicates in the source document. Both the subject and the study staff member must sign/initial the source document to indicate the subject performed the SVSS as instructed.

8.1.6. Vitiligo-Specific Quality of Life Instrument (VitiQoL)

The subject will complete the VitiQoL questionnaire at baseline (Visit 2), Visits 7, 8, 9, 10, Visit 11 (if applicable) and Visit 14 (Week 48) (see Appendix 4). The study staff should instruct the subject to answer the questions based on the impact of vitiligo over the past month. The response to each question will be scored on a 0 (not at all) to 6 (all of the time) continuous bipolar scale.

8.2. Assessment of Safety

Safety will be assessed throughout the study by the investigator or a designated and appropriately trained staff member.

8.2.1. ECGs

Standard 12-lead ECGs will be performed by a qualified staff member at Screening (Visit 1), Baseline (Visit 2), Day 8 (Visit 3), Visits 5-10, Visit 11 (if applicable) and if continuing for the additional visits, Visit 15. The ECGs must be obtained using a standard 12-lead ECG with a 10mm/mV amplitude, at 25mm/sec and a 5-10-second duration. To ensure a steady heart rate the subject must rest quietly in the supine position for at least 5 minutes prior to performing the ECG.

A central lab, eResearchTechnology, Inc. (ERT), will provide ECG equipment, supplies and site training. In addition, ERT will process ECGs received by the sites and report results via a secure study portal. The ECG results will be interpreted by a qualified health professional (evaluator) and the interpretation reported either directly on the tracing or in a separate report. The evaluator will interpret the results of every ECG and define the ECG as “normal” or “abnormal”. Variations such as minor ST changes (*i.e.*, <0.5mm depression) and early re-polarization are considered normal.

The investigator must review the evaluator’s interpretation of each subject’s screening ECG prior to Baseline (Visit 2). The investigator will review, sign and date the evaluator’s interpretation of all ECG reports in a timely manner and comment on the clinical significance of any result that is defined by the evaluator as abnormal.

Any abnormalities that are, in the opinion of the investigator, clinically significant, must be reported as history if found prior to the start of the first study medication application or as an AE if found after the start of the first study medication application (see Section 9.1.1).

8.2.2. Physical Examination

The investigator or designee will perform a physical examination for all body systems (general appearance, examination of head, eyes, ears, nose and throat, respiratory, cardiovascular, abdominal, neurological, musculoskeletal, lymphatic and skin assessment) at Screening (Visit 1) and end of study Week 28 (Visit 11) or if continuing for the additional visits, Week 52 (Visit 15).

Any measure that is, in the opinion of the investigator, abnormal AND clinically significant (CS) must be recorded as history if found prior to the first study medication application or as an AE if found after the first study medication application begins.

8.2.3. Vital signs

Vital signs will be measured at each visit during the study. The following items will be measured:

- Body temperature
- Pulse rate
- Respiration rate
- Blood pressure (systolic and diastolic) after the subject sits quietly for at least 5 minutes
- Height (at Visit 1 only)
- Weight (at Visit 1 only)

Any measure that is, in the opinion of the investigator, abnormal AND clinically significant (CS) must be recorded as history if found prior to the first study medication application, or as an AE if found after the first study medication application begins.

A systolic blood pressure >140mm Hg or a diastolic blood pressure >90 mmHg is considered abnormal and therefore must be defined as CS or not clinically significant (NCS) in the eCRF. A weight >300 lbs. is considered abnormal and therefore must be defined as CS or NCS in the eCRF.

8.2.4. Clinical Laboratory Assessments

At the visits detailed in the Schedule of Assessments, a qualified staff member will collect non-fasting samples for clinical laboratory analysis. Approximately 18.5 ml of blood will be collected at Visit 1 and approximately 10.5 ml for each sample detailed in the Schedule of Assessments a total of approximately 113 ml per subject for Visit 1-11, approximately 42 ml for Visits 12-15, and up to approximately 155 ml for the entire study. Samples will be sent to a central laboratory for analysis. Refer to the study specific laboratory manual for handling and shipping instructions. The following tests will be conducted:

Chemistry Panel	Complete Blood Count
Albumin	Hematocrit
Alkaline phosphatase	Hemoglobin
Alanine aminotransferase (ALT)	Platelet count
Aspartate aminotransferase (AST)	Red blood cell morphology
Blood urea nitrogen (BUN)	Red blood cell count
Bicarbonate	White blood cell count
Calcium	White blood cell differential
Chloride	% & absolute
Creatinine	Basophils
Glucose	Eosinophils
Lactate dehydrogenase (LDH)	Lymphocytes
Phosphorus	Monocytes
Potassium	Neutrophils
Sodium	
Total bilirubin	
	Urinalysis

Total protein
Uric acid
Total cholesterol, LDL, HDL,
Triglycerides
CPK
Screening Only
Virology (HepB, HCV, HIV)
Quantiferon Gold
T3/T4, TSH
Serum pregnancy

The results of the clinical laboratory tests will be reported on the central laboratory's standard reports. The investigator must note NCS or CS to define the clinical relevance of any result that is outside the normal range for the laboratory. The investigator must date and initial every laboratory report.

The investigator or subinvestigator must review all the Screening (Visit 1) laboratory test results against the study entry criteria for each subject prior to Baseline (Visit 2). The investigator must report all laboratory results that are BOTH outside the normal range for the laboratory AND, in the opinion of the investigator, CS as medical history if found prior to the first study medication treatment or as an AE if found after the first study medication treatment begins. The investigator must review all laboratory reports in a timely manner.

8.2.5. Local Tolerability Assessment (LTA)

The LTA is the investigator's assessment of the average overall severity of signs and the subject's assessment of the average overall severity of symptoms associated with an application site reaction on the treated areas of the face. The investigator and subject must NOT refer to any other evaluation to assist with these assessments. This is not a comparison with the assessment at any other time point.

At Visits 2-11, the investigator and the subject will evaluate the LTA signs and the LTA symptoms respectively.

LTA Signs (Investigator or designee assessment):

- Erythema
- Edema
- Scaling/dryness

LTA symptoms (Subject assessment):

- Stinging
- Burning

The investigator will assess the LTA signs as follows:

- At Visit 2:
 - Prior to the first study medication application
 - 20 (± 4) minutes after the application completion time.
- At Visits 3-11.

The subject will assess the LTA symptoms as follows:

- At Visit 2:
 - Prior to the first study medication application report the LTA for each symptom over the previous 24 hours
 - 10 (± 4) minutes after the application completion time report the average severity since the application completion time.
- At Visits 3-11:
 - Report the average LTA for each symptom over the previous 24 hours.

The investigator, for the signs, should report the one integer that best describes the average overall severity on the treatment areas of the face using the scales below:

Local Tolerability Assessment – Erythema

Grade	Descriptor
0	Clear: No erythema present
1	Mild: Slight erythema
2	Moderate: Definite erythema
3	Severe: Marked, fiery erythema

Local Tolerability Assessment – Edema

Grade	Descriptor
0	Clear: No edema present
1	Mild: Slight edema
2	Moderate: Definite edema
3	Severe: Marked edema

Local Tolerability Assessment – Dryness/Scaling

Grade	Descriptor
0	Clear: No signs of dryness or scaling
1	Mild: Slight roughness (may be more easily felt than seen), barely perceptible scaling
2	Moderate: Moderate roughness, definite scaling
3	Severe: Marked roughness, heavy scaling

The subject, for the symptoms, should report the one integer that best describes the average overall severity on the treatment areas of the face using the scales below:

Local Tolerability Assessment – Itching

Grade	Descriptor
0	Clear: No itching
1	Mild: Slight itching, not bothersome

2	Moderate: Definite itching, slightly bothersome
3	Severe: Intense itching, bothersome and/or uncomfortable

Local Tolerability Assessment – Burning/ Stinging

Grade	Descriptor
0	Clear: No burning or stinging
1	Mild: Slight warmth or tingling, not bothersome
2	Moderate: Definite warmth or tingling, slightly bothersome
3	Severe: Intense feeling of heat or tingling, bothersome and/or uncomfortable

Follow these steps to complete the LTA for each symptom by a subject:

- An investigational center staff member, other than the evaluating investigator, will show the appropriate LTA symptom grading scale to the subject and instruct the subject on the time interval to be considered
- The staff member should not give any opinion on the meaning of the LTA descriptors
- The subject should verbally indicate the appropriate grade for each symptom and the staff member will report the grade in the source document
- Both the subject and the staff member must sign/initial the source document to indicate the subject performed the LTA for symptoms as instructed
- The staff member must not influence the subject's assessment.

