- Clarified that a heart rate of ≤ 45 beats/minutes based on the screening ECG should only exclude subjects from randomization, if in the opinion of the investigator the low heart rate is clinically significant.
- Clarified that subjects with any screening values that meet the study interruption criteria must have repeat lab testing performed with results meeting the minimum criteria for resumption,
- Added a specific exclusion criterion for subjects who are positive for HIV, Hepatitis B or C, previously covered under Exclusion Criterion 9: Subjects with a current viral infection,
- Added to Permitted Concomitant Medications, Therapies and Over the Counter Products (OTC) Section: Male subjects who shave at screening and baseline should maintain the same shaving regimen during the study.
- Added to the Prohibited Medications, concomitant use of:
 - Camouflaging agents with a temporary dyeing effect such as dihydroxyacetone, or self-tanners or,
 - Immune boosting herbal supplements such as astragalus
- Deleted 80% total body VASI from Section 6.4.1
- Revised: Timeframe each bottle of study medication should be used from 14 days to 30 days based on updated stability information,
- Added APPENDIX 6, Area of Interest Diagram in order to clarify the areas of the face with vitiligo that can be included in the TBSA calculation.
- Replaced Vitiligo Area Severity Index (VASI) Vitiligo Area Scoring Index (VASI) throughout the protocol.

Administrative Letter #1 Dated 29JAN2018 updated Aclaris Therapeutics, Inc. office location. Administrative Letter #2 Dated 05OCT2018 changed the number of subjects enrolled from 24 to 33. The changes from both Administrative Letters were incorporated into Protocol Amendment 2, Version 3.0 Dated 12OCT 2018.

Protocol Amendment 2 (version 3.0 Dated 12OCT2018) extended the treatment period for an additional 24 weeks of active treatment with a 4-week post-treatment follow-up visit to allow for the timeframe for repigmentation which may require 6 to 12 months of treatment. Protocol Amendment 2 provides the following primary changes to Protocol Amendment 1 (version 2.0 Dated 19JUN2018):

- Added Visit 12 (Week 32), Visit 13 (Week 40), Visit 14 (Week 48), and Visit 15 (Week 52).
- Revised the Primary Efficacy Assessment timepoint to Visit 14, Week 48.

- Added CPK as an additional safety assessment.
- Added the neck as an acceptable treatment area.

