6. INVESTIGATIONAL PLAN

6.1. Overall Study Design

This Phase 2, multicenter, open label study is designed to evaluate the safety, tolerability and efficacy of ATI-50002 Topical Solution in subjects with facial non-segmental vitiligo. Subjects will be required to have a clinical diagnosis of new onset or actively progressing non-segmental facial vitiligo involving at least 0.25% TBSA (excluding upper and lower eyelids, mucosal lip areas, beard [if applicable]; and forehead and chin areas covered by the stereotactic positioning device for photography) with at least one area of the face with normal pigmentation. The face is defined as the area from the border of the hairline, not including hair bearing skin to the jawline. Thirty-three subjects will receive ATI-50002 Topical Solution, 0.46%, BID for up to 48 weeks.

During the screening period, subjects will be assessed for eligibility to receive study medication. Eligible subjects will apply study medication to the vitiliginous areas of the face and neck including $\frac{1}{2}$ " margin around these areas (excluding the upper and lower eyelids and mucosal areas of the lips) twice-a-day for up to 48 weeks. Assessment of response to treatment will be performed using the Canfield 2-D Photographic image analysis, Facial VASI, Vitiligo Noticeability Scale, VitiQoL, and Subject Vitiligo Satisfaction Scale. These assessments will occur as specified in the Schedule of Assessments. Subjects will be seen at up to 15 study visits, including up to 48 weeks of active treatment followed by 4 weeks of post treatment follow-up.

Safety and tolerability will be evaluated throughout the study by assessment of electrocardiograms (ECG), clinical laboratory tests, adverse events including local site reactions and vital signs.

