7.3. Application of Study Medication

Subjects will be instructed to apply a thin film of ATI-50002 Topical Solution, up to 2-mL, twice-daily; once in the morning and approximately 8-12 hours later to the vitiliginous areas of the face and neck including a $\frac{1}{2}$ " inch margin around these areas (excluding: the area from the bony rim of the orbit to and including the upper and lower eyelids; and mucosal lip areas) following the instructions in APPENDIX 1. The subject must wash her/his hands thoroughly before and after each study drug application. At each study visit, subjects should bring the study medication including unused bottles. The disposable applicators should be disposed of at the subject's home out of the reach of children.

Following review of study medication instructions, subjects will apply the first dose of study medication in the office under the instruction and supervision of the study staff.

During the Baseline visit (Visit 2), the study staff member will:

- Dispense the appropriate study medication bottle.
- Weigh the bottle with the cap prior to the first study medication application.
- Instruct the subject on the appropriate application technique following instructions in APPENDIX 1.
- Observe the subject's first study medication application to ensure proper coverage and monitor the subject for at least 20 minutes.
- After the first application, the study staff should weigh the study bottle with the cap.
- Dispense the study medication to the subject.
- Provide feedback on the application procedure, if needed.

If the subject develops a new patch of vitiligo on the face or neck during the study, the investigator or designee will instruct the subject to treat the new area of facial vitiligo. The investigator must incorporate the new area of facial vitiligo, once it is clinically evident, into the F-VASI assessment. New areas of vitiligo on the face or other body areas that develop during the study are not considered adverse events.

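### The Local Tolerability Assessment gives no grade for the treated neck, and its symptom list does not match its printed scales

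*Combined protocol and SAP*

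**What the plan says.** **Where drug is applied.** Section 6.1 states: "Eligible subjects will apply study medication to the vitiliginous areas of the face and neck". Section 7.3 has the second daily application "approximately 8-12 hours later to the vitiliginous areas of the face and neck". Appendix 1 repeats this for the neck where applicable. The amendment history lists under Amendment 2: "Added the neck as an acceptable treatment area".

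**What the LTA covers.** Section 8.2.5 defines the LTA as the investigator's grading of signs and the subject's grading of symptoms "associated with an application site reaction on the treated areas of the face". The investigator's and the subject's instructions each ask for the "average overall severity on the treatment areas of the face using the scales below". The section does not mention the neck.

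**Which symptoms.** Under "LTA symptoms (Subject assessment" the section lists stinging and burning. The scales that follow the subject's instruction are headed "Local Tolerability Assessment – Itching" and "Local Tolerability Assessment – Burning/ Stinging".

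**How the data are used.** Tolerability is part of the primary objective (Section 4.1). Section 11.2 plans a summary of LTA change from baseline to Visit 10. The LTA is performed at Visits 2 to 11.

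**The concern.** Local tolerability follows the drug. A focus on facial vitiligo can justify efficacy measures limited to the face, but it does not by itself explain why an application-site assessment leaves out an application site. Sections 5.6 and 5.6.1 do refer to treated neck areas, so the face-only wording in Section 8.2.5 looks like text that was not carried through when the neck was added. The documents do not confirm that.

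In a single-arm, open-label study no control group offsets an incomplete measurement. If the LTA is reported as the local tolerability of the product, a reader will assume that it covers every treated site and a defined set of symptoms. As written, it covers neither with certainty.

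**Working it through.** The plan gives no figure to reproduce on this point, and Section 11.1 states that no formal power calculation was done. The check is a comparison of the texts.

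**1. Anatomical scope.**

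| Text | Region |
|---|---|
| Application (6.1, 7.3, Appendix 1) | Face and neck |
| LTA definition (8.2.5) | Treated face |
| Investigator's instruction (8.2.5) | Treated face |
| Subject's instruction (8.2.5) | Treated face |

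All three LTA statements stop at the face. A rater who follows them scores 0 on every item for a subject whose only reaction is on the treated neck.

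**2. Item set.**

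| | Listed | Scales printed |
|---|---|---|
| Signs | Erythema; edema; scaling/dryness | Erythema; edema; dryness/scaling |
| Symptoms | Stinging; burning | Itching; burning/stinging combined |

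The three signs match their three scales. The symptoms do not: one of the two scales (itching) has no entry in the list, and the two listed items share the other scale. The procedure at the end of 8.2.5 tells staff to show the appropriate scale and record a grade for each symptom, without naming the symptoms. It does not settle the matter.

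**3. Other routes of capture.** Section 6.1 counts local site reactions among adverse events, and Section 7.6 recognises application-site adverse events. Neither is limited to the face. Under Section 9.2.1 adverse events are elicited by a non-directive question, with directed follow-up where appropriate. Section 9.1.5 grades them on a different severity scale. By definition, grade 1 on both LTA symptom scales is not bothersome, which is the kind of reaction a general health question may miss. Adverse event records also give no neck LTA baseline or change score.

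**4. Direction of any effect.** The LTA grade is an average over the treated area. Take two hypothetical subjects on the 0 to 3 scale:

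- Face 0, neck 2: face-only grading gives 0, while an average over both regions would exceed 0.
- Face 2, neck 0: face-only grading gives 2, while an average over both regions would be below 2.

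Face-only scores can therefore lie below or above a score for all treated skin.

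**5. Size.** The number of subjects treated on the neck is not stated. With 33 planned, it could be anything from 0 to 33.

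**The case against.** A reader might infer that local reactions are under-recorded in this trial. The documents do not support that. Neck reactions are reportable as adverse events with no restriction to the face, directed questions may follow the opening question, and a marked reaction is what that route is suited to catch. What is lost is a structured 0 to 3 grade, chiefly for mild reactions.

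A reader might also infer that itching is not collected. The subject's instruction points to the scales that follow, and the first of these is itching, so itching is probably graded. The source form and eCRF are not in the documents, and Section 12.1 provides for training on the protocol and eCRFs. Divergence between sites is a risk, not a finding. Stinging and burning are both graded; only their separation is lost.

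Third, a bias toward good tolerability is tempting to claim but does not follow, because the LTA is an average.

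Finally, this is a pilot with descriptive statistics, and the dose-modification, interruption and discontinuation criteria in Sections 7.6, 9.2.3 and 9.2.4 do not refer to LTA grades. That limits the consequence.

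All of this stands, but it does not remove the two mismatches. The adverse event route cannot fill a neck LTA summary, and the symptom variables still need a definition.

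**Conclusion.** The point holds in limited form. Followed as written, the LTA gives no structured grade at one treated site, so its summary describes the face only. The symptom items are ambiguous because the list and the scales disagree.

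Both mismatches are plain in the text and rest on no numerical assumption. The consequence is possible incompleteness or inconsistency in the LTA data. Neither a shown loss of safety information nor a known direction of bias follows. The extent of the neck gap depends on how many subjects treat the neck and how many LTA visits they still had when they began; the documents give neither. The passages should be reconciled because tolerability is in the primary objective and LTA change is a planned summary.

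**What to change.** In Section 8.2.5:

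- For subjects treated on the neck, record the LTA signs and symptoms for the neck separately from the face. Keep the average-severity definition within each region.
- Make the symptom list match the printed scales: itching, and burning/stinging.
- Align the source form and eCRF with both changes.

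Separate recording is preferable to one score taken from the worse region. A worst-region score would contradict the averaging definition and, in subjects with a face-only baseline, would subtract unlike quantities in the change-from-baseline summary. Separate recording leaves face scores comparable with those already collected.

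**Cost.** No new visit or assessor is needed. The added entry is 3 signs + 2 symptom scales = 5 grades per LTA occasion. There are at most 2 (before and after application at Visit 2) + 9 (Visits 3 to 11) = 11 occasions, so up to 5 × 11 = 55 grades per neck-treated subject. Neck change from baseline can be computed only for subjects with a neck baseline; other neck scores should be summarised by visit, and the report should state when neck grading began.
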